- Induction Cohort B3 (Dose Level 3): Venetoclax: 800 mg/QD NC on Days 1–7 Atezolizumab: 1200 mg Q3W on Day 1 Carboplatin: AUC 5 mg/mL min (Calvert formula) on Day 1 Etoposide: 100 mg/m² on Days 1–3
- Induction Cohort B4 (Dose Level 4): Venetoclax: 800 mg/QD NC on Days 1–14 Atezolizumab: 1200 mg Q3W on Day 1 Carboplatin: AUC 5 mg/mL min (Calvert formula) on Day 1 Etoposide: 100 mg/m² on Days 1–3

Figure 4 Study Schema: Dose-Escalation, Induction (Arm B)

Note: Cohorts may incorporate primary prophylactic growth factor support as described below and in Section 3.1.4.

DLT = dose-limiting toxicity; MTD = maximum tolerated dose; NC = non-continuous; RP2D-I = recommended Phase II dose for induction.

Patients may be treated in up to five NC dosing cohorts (i.e., venetoclax 200 mg Days 1–7 NC, 400 mg Days 1–7 NC, 800 mg Days 1–7 NC, 800 mg Days 1–14 NC, and any of the dose levels integrating primary prophylactic growth factor support). Specifically, at the initiation of the induction phase of dose–escalation Arm B, cohorts will be treated without primary prophylactic growth-colony stimulating factor (G-CSF). If 2 or more patients out of the first 6 DLT-evaluable patients in a particular cohort without primary prophylactic growth factor support experienced neutropenia-related adverse events (Grade 4 neutropenia resulting in treatment delay beyond 14 days or Grade 3–4 febrile neutropenia), then that particular cohort level will be tested again at the same dose *level* with mandatory primary prophylactic growth factor support (see Section 3.1.4 for additional details). Of note, primary G-CSF prophylaxis is only mandated during induction and not during maintenance therapy. Such cohorts will be designated with "-P" to denote the primary G-CSF prophylactic requirement (e.g., Cohort B1-P). Subsequent dose–escalation cohorts will then be required to incorporate primary G-CSF prophylaxis.

Patients will be treated for a total of 4 cycles of study treatment for induction. Each cycle will consist of 21 days. Dose-escalation will continue until DLTs are observed. If there is excessive toxicity and DLTs at the lowest tested venetoclax dose in induction, then venetoclax will be subsequently expanded in the maintenance setting only.

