5.1.5.1 Venetoclax Dose Modifications

Although patients with adverse events are to be managed according to the particular clinical circumstances based on the investigator's medical judgment, dose reduction of venetoclax by one and, if needed, two dose levels will be allowed depending on the type and severity of the toxicity encountered (see Table 6). Each dose reduction of venetoclax will occur by 200 mg (e.g., the starting dose of 800 mg will be reduced to 600 mg, then to 400 mg). Dose reduction by two dose levels (e.g., reducing from 800 mg to 400 mg directly) is not permitted. Such patients may continue to receive atezolizumab plus carboplatin and etoposide at the discretion of the investigator in the induction phase and atezolizumab as a single agent in the maintenance phase. Patients requiring clarification regarding management of adverse events and dosing and all patients requiring more than two dose reductions should be discussed with the Medical Monitor. All dose modifications/adjustments must be clearly documented in the patient's source notes and eCRF.

Once a dose has been reduced for a given patient, all subsequent cycles should be administered at the reduced dose level, unless further dose reduction is allowed. Dose re-escalation is not allowed.

Venetoclax Current Dose Level	Venetoclax Dose Reduction
800 mg	600 mg
600 mg	400 mg
400 mg	200 mg
200 mg	100 mg
100 mg	Discontinue venetoclax

Table 6 Venetoclax Dose Reduction

5.1.5.2 Atezolizumab Dose Modification, Treatment Delays, or Treatment Discontinuation and Management of Specific Adverse Events

There will be no dose reduction for atezolizumab in this study. Patients may temporarily suspend study treatment with atezolizumab for up to 105 days beyond the last dose if they experience an adverse event that requires a dose to be withheld. If atezolizumab is withheld because of adverse events for more than 105 days beyond the last dose, then the patient will be discontinued from atezolizumab/ treatment. Exceptions require Medical Monitor approval.

If a patient must be tapered off steroids used to treat adverse events, atezolizumab may be withheld for additional time beyond 105 days from the last dose until steroids are discontinued or reduced to prednisone dose (or dose equivalent) \leq 10 mg/day. The acceptable length of interruption will depend on agreement between the investigator and the Medical Monitor.

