Neutropenia, Grade 3 (ANC < 1000–500/mm³) ^a	 Withhold venetoclax. If counts recover to ANC 1500/mm³: Resume treatment with venetoclax at previous dose. Administer atezolizumab plus carboplatin and etoposide at previous dose during induction treatment. .
Neutropenia, Grade 4 (ANC count < 500/mm ³) ^a	 Withhold venetoclax. Withhold atezolizumab plus carboplatin and etoposide. Administer treatment including G-CSF or growth factors for neutropenia as indicated or as per institutional guidelines. If counts recover to ANC 1500/mm³: Resume venetoclax at one dose level reduction (see Table 6). Administer carboplatin and etoposide at 75% of previous dose (see Table 7). Dose of carboplatin and etoposide can be re-escalated (even to full dose) in subsequent cycles with the approval of Medical Monitor (see Section 5.1.5.2). Administer atezolizumab at previous dose level. If patient develops recurrent Grade 4 neutropenia despite growth factor support and following venetoclax dose reduction to 100 mg and two dose reductions for carboplatin etoposide, discontinue venetoclay and carboplatin etoposide during the induction phase
Febrile neutropenia, Grade 3-4 (ANC < 1000/μL) plus fever of > 38.5°C	 Withhold venetoclax. Withhold atezolizumab plus carboplatin and etoposide. Administer treatment with growth factors per institutional guidelines. Upon resolution of Grade ≥ 3 febrile neutropenia (ANC > 1500/mm³): Resume venetoclax at one dose level reduction (see Table 6). Administer carboplatin and etoposide at 75% of previous dose (see Table 7). Dose of carboplatin and etoposide can be re-escalated (even to full dose) in subsequent cycles with the approval of Medical Monitor (see Section 5.1.5.2). Administer atezolizumab at previous dose level. If patient develops recurrent Grade -34 febrile neutropenia despite growth factor support and following venetoclax dose reduction to 100 mg and two dose reductions for carboplatin etoposide, discontinue venetoclax and carboplatin etoposide during the induction phase.

Table 10Management Guidelines for Specific Adverse Events with
Venetoclax, Atezolizumab, and Carboplatin Etoposide (cont.)

Event	Management		
Thrombocytopenia, Grade 3 (platelet count	 Withhold venetoclax. Withhold atezolizumab plus carbonlatin etoposide 		
< 50,000–25,000/μL) with	• If platelet count recovers to $> 100 000/mm^3$):		

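### The venetoclax step-size rule conflicts with Table 6, and for an 800 mg induction start Table 10 and Section 5.1.5.3 give opposite instructions on chemotherapy at a third severe cytopenia

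*Combined protocol and SAP*

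**What the plan says.** **Section 5.1.5.1** sets the step: "Each dose reduction of venetoclax will occur by 200 mg". On how many steps, it says that "dose reduction of venetoclax by one and, if needed, two dose levels will be allowed". It also says "Dose reduction by two dose levels (e.g., reducing from 800 mg to 400 mg directly) is not permitted", that "all patients requiring more than two dose reductions should be discussed with the Medical Monitor", and "Dose re-escalation is not allowed". Table 6, in the same section, runs 800, 600, 400, 200, 100 mg and then discontinuation.

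**Table 10 (Section 5.1.6.3)** has four cytopenia rows with a joint stopping condition: Grade 4 neutropenia, Grade 3–4 febrile neutropenia, Grade 3 thrombocytopenia with bleeding, and Grade 4 thrombocytopenia. In each, venetoclax and carboplatin/etoposide are discontinued in induction when the event recurs "following venetoclax dose reduction to 100 mg and two dose reductions for carboplatin etoposide". Until then, treatment is withheld and, on recovery, venetoclax resumes one level lower. Chemotherapy resumes at 75% of the previous dose, or 50% in the bleeding row. Footnote a, on the Grade 4 neutropenia and Grade 4 thrombocytopenia rows, ties modifications to Day 1 counts.

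**Section 5.1.5.3** discontinues carboplatin or etoposide for any Grade 3 or 4 toxicity occurring after two dose reductions, whatever the venetoclax dose.

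**Section 3.1.2.2** fixes the length of induction: "Patients will be treated for a total of 4 cycles of study treatment for induction". Cohort B3 is "Venetoclax: 800 mg/QD NC on Days 1–7", and B4 gives the same daily dose on Days 1–14.

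**The concern.** A site managing recurrent severe cytopenia is sent by Section 5.1.6.3 to Sections 5.1.5.1 to 5.1.5.3 and Table 10 together, with no order of precedence. Three things do not fit:

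- The step-size sentence and the last reducing row of Table 6 cannot both hold.
- Patients who need more than two reductions are referred to the Medical Monitor, but the text does not say whether they continue down Table 6. Table 10 presumes that they do.
- The Table 10 stopping condition depends on a dose level that some starting doses reach within induction and others ordinarily do not. Section 5.1.5.3 stops chemotherapy with no such condition.

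At stake is consistent handling of recurrent Grade 4 cytopenia at the highest induction dose. That bears on patient safety, on the exposure and discontinuation summaries (Sections 6.2 and 6.4.1), and on the aggregate safety data used to choose the induction RP2D (Section 3.1.4).

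**Working it through.** **Inputs.** Dose ladder from Table 6; one level at a time from Section 5.1.5.1; four induction cycles and starting doses of 200, 400 and 800 mg from Section 3.1.2.2; Day 1 decisions from Table 10, footnote a; 75% chemotherapy step from Tables 7 and 10.

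**1. The 200 mg step against Table 6.** Differences down the ladder:

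- 800 − 600 = 200
- 600 − 400 = 200
- 400 − 200 = 200
- 200 − 100 = 100

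The rule reproduces the first three rows. Applied to 200 mg it gives 200 − 200 = 0, where Table 6 gives 100 mg.

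**2. When the Table 10 condition can first be met.** Let k be the number of reductions from the starting dose to 100 mg. With one level per cycle, 100 mg first applies in Cycle 1 + k. Two chemotherapy reductions are first in place in Cycle 1 + 2 = 3. The earliest cycle for the triggering recurrence is the larger of 1 + k and 3.

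| Start (mg) | k | Dose in Cycles 1–4 (mg) | First cycle at 100 mg | Earliest triggering cycle |
|---|---|---|---|---|
| 800 | 4 | 800, 600, 400, 200 | 5 | 5 (beyond induction) |
| 400 | 2 | 400, 200, 100, 100 | 3 | 3 |
| 200 | 1 | 200, 100, 100, 100 | 2 | 3 |

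The number of episodes needed is the larger of k and 2, plus the recurrence: 5, 3 and 3. The 200 mg start needs three, not two, because two chemotherapy reductions are also required. That path assumes venetoclax stays at 100 mg after the second episode. If the last row of Table 6 is applied there instead, venetoclax stops alone at the second episode while the joint condition still waits for the third. This too needs settling.

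**3. Sensitivity for 800 mg.** One extra reduction anywhere in induction brings 100 mg forward to Cycle 1 + (4 − 1) = 4. Two extra bring it to Cycle 3.

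**4. Third Grade 4 cytopenia from an 800 mg start, one event per cycle.**

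| Cycle | Venetoclax (mg) | Chemotherapy (fraction of full dose) |
|---|---|---|
| 1 | 800 | 1.00 |
| 2 | 600 | 0.75 |
| 3 | 400 | 0.75 × 0.75 = 0.5625 |

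At the event in Cycle 3, chemotherapy has been reduced twice. Section 5.1.5.3 therefore stops it. Table 10's condition is not met, because venetoclax is at 400 mg. The row instead resumes venetoclax at 200 mg and chemotherapy at 75% of the previous dose (0.75 × 0.5625 = 0.4219 of full dose). From a 400 mg start the two provisions agree on chemotherapy at the same event, because venetoclax is already at 100 mg.

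**The case against.** The best defence is that these are guidelines with room for judgement, and that other rules protect the patient. Much of that is right, and it rules out several stronger readings.

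- **That more than two reductions are forbidden.** The sentence allowing up to two levels and the sentence barring a two-level drop can be read together as two successive single steps. Further reductions go to the Medical Monitor; they are not barred. Table 6 also needs more rows than one patient would use, since it serves several starting doses. What stands is that the text does not say what happens after the referral.
- **That 100 mg can never be reached from 800 mg.** Section 5.1.5 lets the investigator accelerate the guidelines. Section 4.3.2 does not count cycles without chemotherapy, and Section 4.3.2.3 lets venetoclax continue while chemotherapy is delayed. The febrile neutropenia and Grade 3 thrombocytopenia rows lack footnote a, and uncontrolled Grade 4 diarrhea has a further one-level reduction. One extra step is enough to reach 100 mg in Cycle 4. None of these is the ordinary route, though. Acceleration meets the ban on direct two-level drops. The four cytopenia rows withhold venetoclax together with chemotherapy, so they do not ordinarily create venetoclax-only cycles. Section 4.3.2.3 recommends giving a delayed study drug at the next scheduled cycle. The diarrhea step depends on an unrelated event.
- **That stopping is left without any rule.** Section 4.6.1 requires discontinuation for intolerable related toxicity, Section 5.1.5.3 stops chemotherapy, and Table 10 withholds and reduces at each episode. This stands, but it is also the source of the conflict, since Section 5.1.5.3 and Table 10 disagree at the third event.
- **That the trigger alters DLT counts.** Permanent discontinuation of a study drug is a DLT criterion, so the link is tempting. The DLT window closes on Day 1 of Cycle 2 (Section 3.1.3), and the trigger needs a recurrence in Cycle 3 or later from every starting dose.

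**Conclusion.** The point holds in three parts. First, the 200 mg step rule and the 200 to 100 mg row of Table 6 contradict each other outright. Second, under the default rules a patient starting at 800 mg (B3, B4, or expansion at an 800 mg induction RP2D) ends induction at 200 mg, one level short of the Table 10 condition, whereas starts of 400 and 200 mg can meet it at the third episode. Third, at a third Grade 4 cytopenia from 800 mg, Section 5.1.5.3 stops chemotherapy and Table 10 resumes it at 75% of the previous dose.

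The second and third parts rest on one level per cycle, Day 1 decisions, four counted cycles and no extra reduction for another toxicity. They arise only if escalation reaches 800 mg. The first part needs none of these assumptions. MTD, DLT counts, sample size and error rates are untouched. This is still more than clerical, because two provisions give opposite instructions for the same patient.

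**What to change.** Reconcile Sections 5.1.5 to 5.1.5.3, including Table 6, with Table 10 so that they state one step size for each level, what happens after the second reduction once the Medical Monitor is consulted, and the point of discontinuation of venetoclax and of chemotherapy for each starting dose. State which provision governs where Section 5.1.5.3 and Table 10 both apply, and how the investigator's latitude to accelerate sits with the ban on direct two-level drops. In the same edit, correct the diarrhea rows of Table 10, which cite the chemotherapy table (Table 7) for the venetoclax reduction. Which dose or stopping rule is right is for the sponsor's clinical team; none is proposed here.

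The cost is protocol wording in a few paragraphs and two tables. No design, sample size or analysis changes follow.

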5.1.6 Management Guidelines

5.1.6.1 Management of Venetoclax-Specific Adverse Events

Refer to Appendix 12 for details on management of venetoclax-specific adverse events.

5.1.6.2 Management of Atezolizumab-Specific Adverse Events

Refer to Appendix 13 for details on the management of atezolizumab-specific adverse events, including systemic immune activation. See Appendix 8 for anaphylaxis precautions.

5.1.6.3 Management of Potential Overlapping Toxicities

The main overlapping toxicities based on the individual safety profile of venetoclax and atezolizumab, carboplatin, and etoposide are expected to be hematologic toxicities such as neutropenia, febrile neutropenia, and thrombocytopenia (in the case of venetoclax, etoposide and carboplatin); and gastrointestinal toxicities such as diarrhea, nausea, and vomiting (in the case of venetoclax, atezolizumab, etoposide and carboplatin).

Table 10 below provides management guidelines for specific overlapping toxicities with venetoclax, atezolizumab and carboplatin etoposide. Nevertheless, the attribution and management of certain adverse events that have been associated with each agent separately (e.g., hepatotoxicity, skin and gastrointestinal toxicity) may be unclear when the agents are administered together. It is theoretically possible that allergic or inflammatory adverse events associated with carboplatin and etoposide (e.g., dermatitis, infusion-associated symptoms) could be exacerbated by the immunostimulatory activity of atezolizumab.

Toxicities should initially be managed according to the recommendations in Sections 5.1.5.1–5.1.5.3, Table 10, Appendix 12, and Appendix 13 with dose holds and modifications (if applicable) applied to the component of the study drug judged to be the primary cause. For severe (Grade 3) or persistent Grade 1–2 diarrhea, an endoscopic evaluation should be considered. Additional tests, such as autoimmune serology or biopsies, may be used to determine a possible immunogenic etiology for adverse events listed above. If, in the opinion of the investigator, atezolizumab is a potential inciting factor, the dose of atezolizumab may be held for a maximum of 105 days beyond the last infusion (see Section 5.1.5.2). Exceptions require Medical Monitor approval. Prompt symptomatic management is appropriate for mild immune-mediated adverse events. In severe cases, immune-mediated toxicities may be acutely managed with systemic corticosteroids or TNF- α inhibitors. These cases should be discussed with the Medical Monitor.

Table 10Management Guidelines for Specific Adverse Events with
Venetoclax, Atezolizumab, and Carboplatin Etoposide

Event	Management
Neutropenia, Grade 3 (ANC < 1000–500/mm³) ^a	 Withhold venetoclax. If counts recover to ANC 1500/mm³: Resume treatment with venetoclax at previous dose. Administer atezolizumab plus carboplatin and etoposide at previous dose during induction treatment. .
Neutropenia, Grade 4 (ANC count < 500/mm ³) ^a	 Withhold venetoclax. Withhold atezolizumab plus carboplatin and etoposide. Administer treatment including G-CSF or growth factors for neutropenia as indicated or as per institutional guidelines. If counts recover to ANC 1500/mm³: Resume venetoclax at one dose level reduction (see Table 6). Administer carboplatin and etoposide at 75% of previous dose (see Table 7). Dose of carboplatin and etoposide can be re-escalated (even to full dose) in subsequent cycles with the approval of Medical Monitor (see Section 5.1.5.2). Administer atezolizumab at previous dose level. If patient develops recurrent Grade 4 neutropenia despite growth factor support and following venetoclax dose reduction to 100 mg and two dose reductions for carboplatin etoposide, discontinue venetoclay and carboplatin etoposide during the induction phase
Febrile neutropenia, Grade 3-4 (ANC < 1000/μL) plus fever of > 38.5°C	 Withhold venetoclax. Withhold atezolizumab plus carboplatin and etoposide. Administer treatment with growth factors per institutional guidelines. Upon resolution of Grade ≥ 3 febrile neutropenia (ANC > 1500/mm³): Resume venetoclax at one dose level reduction (see Table 6). Administer carboplatin and etoposide at 75% of previous dose (see Table 7). Dose of carboplatin and etoposide can be re-escalated (even to full dose) in subsequent cycles with the approval of Medical Monitor (see Section 5.1.5.2). Administer atezolizumab at previous dose level. If patient develops recurrent Grade -34 febrile neutropenia despite growth factor support and following venetoclax dose reduction to 100 mg and two dose reductions for carboplatin etoposide, discontinue venetoclax and carboplatin etoposide during the induction phase.

Table 10Management Guidelines for Specific Adverse Events with
Venetoclax, Atezolizumab, and Carboplatin Etoposide (cont.)

Event	Management		
Thrombocytopenia, Grade 3 (platelet count	 Withhold venetoclax. Withhold atezolizumab plus carbonlatin etoposide 		
< 50,000–25,000/μL) with	• If platelet count recovers to $> 100 000/mm^3$):		
Grade ≥ 2 bleeding	 Resume venetoclax at one dose level reduction (see Table 6). Administer carboplatin and etoposide at 50% of previous dose (see Table 7). Dose of carboplatin and etoposide can be re-escalated (even to full dose) in subsequent cycles with the 		
	approval of Medical Monitor (see Section 5.1.5.2).		
	 Administer atezolizumab at previous dose level. 		
	 If patient develops recurrent Grade 3 thrombocytopenia with Grade ≥ 2 bleeding following venetoclax dose reduction to 100 mg and two dose reductions for carboplatin etoposide, discontinue venetoclax and carboplatin etoposide during the induction phase. 		
Thrombocytopenia, Grade 4	Withhold venetoclax.		
(platelets < 25,000/µL) ^a	Withhold atezolizumab plus carboplatin and etoposide.		
	 Administer platelet transfusion if platelet count is <10,000/µL or as per institutional guidelines. 		
	 If platelet count rises to ≥ 100,000/mm³: 		
	 Resume venetoclax at one dose level reduction (see Table 6). Administer carboplatin and etoposide at 75% of previous dose (see Table 7). Dose of carboplatin and etoposide can be re-escalated (even to full dose) in subsequent cycles with the approval of Medical Monitor (see Section 5.1.5.2). 		
	 Administer atezolizumab at previous dose level. 		
	 If patient develops recurrent Grade 4 thrombocytopenia following venetoclax dose reduction to 100 mg and two dose reductions for carboplatin etoposide, discontinue venetoclax and carboplatin etoposide during the induction phase. 		
Diarrhea, Grade 3	Withhold venetoclax.		
	Withhold atezolizumab plus carboplatin and etoposide.		
	Administer anti-diarrheals per institutional guidelines (e.g.		
	loperamide 4 mg initial dose up to a maximum of 16 mg per day)		
	• Upon resolution of Grade 3 diarrhea to Grade ≤ 1:		
	 Resume treatment with venetoclax at the previous dose. Administer carboplatin and etoposide at previous dose (see Table 8). Administer ategolizumab at previous dose level 		

Event	Management
Diarrhea, Grade 3 (cont.)	 For uncontrolled Grade 3 diarrhea that occurs on adequate anti- diarrhea medication or any grade of diarrhea requiring hospitalization: Reduce venetoclax by one dose level (see Table 7). Administer carboplatin and etoposide at 75% of previous dose (see Table 8). Dose of carboplatin and etoposide can be re-escalated (even to full dose) with the approval of Medical Monitor (see Section 5.1.5.2). Administer atezolizumab at previous dose.
Diarrhea, Grade 4	 Withhold venetoclax. Withhold atezolizumab plus carboplatin etoposide. Administer anti-diarrheals per institutional guidelines (e.g., loperamide 4 mg initial dose up to a maximum of 16 mg per day) Upon resolution of Grade 4 diarrhea to Grade ≤ 1: Resume treatment with venetoclax at one dose level reduction (see Table 7) Administer carboplatin and etoposide at 75% of previous dose (see Table 8). Dose of carboplatin and etoposide can be re-escalated (even to full dose) with the approval of Medical Monitor (see Section 5.1.5.2). Administer atezolizumab at previous dose. For uncontrolled Grade 4 diarrhea that occurs despite adequate anti-diarrhea medication or any grade of diarrhea requiring hospitalization: Further reduce venetoclax by one dose level (see Table 7). Administer carboplatin and etoposide at 75% of previous dose (see Table 8).
Hepatic event, Grade 2	 Monitor LFTs more frequently until return to baseline Events of > 5 days duration: Withhold atezolizumab for up to 12 weeks after event onset. Initiate treatment with corticosteroids equivalent to 1–2 mg/kg/day oral prednisone. If event resolves to Grade 1 or better, resume atezolizumab. If event does not resolve to Grade 1 or better while withholding atezolizumab, permanently discontinue atezolizumab and contact Medical Monitor.

Table 10Management Guidelines for Specific Adverse Events with
Venetoclax, Atezolizumab, and Carboplatin Etoposide (cont.)

Table 10 Management Guidelines for Specific Adverse Events with Venetoclax, Atezolizumab, and Carboplatin Etoposide (cont.)

Event	Management	
Hepatic event, Grade 3	 Discontinue atezolizumab. Withhold venetoclax. Withhold carboplatin and etoposide. If hepatic event resolves to ≤ Grade 1: Resume venetoclax at one dose level reduction (see Table 6). Administer carboplatin and etoposide at 75% of previous dose (see Table 8). 	
Hepatic event, Grade 4	Discontinue atezolizumab.Discontinue venetoclax.Discontinue carboplatin and etoposide.	

ANC = absolute neutrophil count; G-CSF = growth-colony stimulating factor.

^a Dose modifications (as specified in the table above) should be made based on ANC and platelet count assessment on Day 1 of each cycle. No dose modifications are required based on ANC and platelet count assessment done on Cycle 1, Day 8 and Cycle 1, Day 15.

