4.3.2.1 Atezolizumab

All patients will receive 1200 mg atezolizumab administered by IV infusion on Day 1 of each 21-day cycle. The atezolizumab dose is fixed and is not dependent on body weight. Atezolizumab infusions will be administered per the instructions outlined in Table 2.

No dose modification for atezolizumab is allowed. Guidelines for treatment interruption or discontinuation are provided in Appendix 10 and Appendix 13. Guidance on study drug administration in the context of management of specific adverse events is provided in Section 5.

For further details on dose preparation, storage, and administration instructions for atezolizumab, please refer to the pharmacy manual and/or the Atezolizumab Investigator's Brochure.

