4.3.2.3 Atezolizumab/Venetoclax

The following rules apply as long as neither atezolizumab nor venetoclax has been permanently discontinued:

- Treatment cycles will normally begin with dosing of atezolizumab on Day 1 of each 21-day cycle. If atezolizumab is delayed for related toxicity, it is recommended that the venetoclax is also delayed. However, if venetoclax is delayed for related toxicity, atezolizumab may be continued, if considered appropriate at the discretion of the investigator.
- In case of delays in dosing of one study drug (atezolizumab or venetoclax) for drug-related toxicity while the other study drug (atezolizumab or venetoclax) is given as planned, it is recommended that the study drug being delayed be administered at the next scheduled infusion (i.e., at the next scheduled 21-day cycle).

Carboplatin and/or etoposide may be administered as planned in the event that atezolizumab and/or venetoclax dose(s) are delayed. If carboplatin and/or etoposide doses must be delayed, atezolizumab and/or venetoclax may be administered as planned.

Guidelines for treatment interruption or discontinuation are provided in Sections 4.6.1 and 5.1.5.

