Diarrhea or colitis, Grade 4	 Permanently discontinue atezolizumab and contact Medical Monitor.^c Refer patient to GI specialist for evaluation and confirmation biopsy. Initiate treatment with corticosteroids equivalent to 1–2 mg/kg/day IV methylprednisolone and convert to 1–2 mg/kg/day oral prednisone or equivalent upon improvement. If event does not improve within 48 hours after initiating corticosteroids, consider adding an immunosuppressive agent. If event resolves to Grade 1 or better, taper corticosteroids over ≥ 1 month.

GI = gastrointestinal.

^a Atezolizumab may be withheld for a longer period of time (i.e., > 12 weeks after event onset) to allow for corticosteroids (if initiated) to be reduced to the equivalent of ≤ 10 mg/day oral prednisone. The acceptable length of the extended period of time must be agreed upon by the investigator and the Medical Monitor.

^b If corticosteroids have been initiated, they must be tapered over ≥ 1 month to the equivalent of ≤ 10 mg/day oral prednisone before atezolizumab can be resumed.

^c Resumption of atezolizumab may be considered in patients who are deriving benefit and have fully recovered from the immune-mediated event. Patients can be re-challenged with atezolizumab only after approval has been documented by both the investigator (or an appropriate delegate) and the Medical Monitor.

ENDOCRINE EVENTS

Thyroid disorders, adrenal insufficiency, diabetes mellitus, and pituitary disorders have been associated with the administration of atezolizumab. Management guidelines for endocrine events are provided in Table 4.

Patients with unexplained symptoms such as headache, fatigue, myalgias, impotence, constipation, or mental status changes should be investigated for the presence of thyroid, pituitary, or adrenal endocrinopathies. The patient should be referred to an endocrinologist if an endocrinopathy is suspected. Thyroid-stimulating hormone (TSH) and free triiodothyronine and thyroxine levels should be measured to determine whether thyroid abnormalities are present. Pituitary hormone levels and function tests (e.g., TSH, growth hormone, luteinizing hormone, follicle-stimulating hormone, testosterone, prolactin, adrenocorticotropic hormone [ACTH] levels, and ACTH stimulation test) and MRI of the brain (with detailed pituitary sections) may help to differentiate primary pituitary insufficiency from primary adrenal insufficiency.

Event	Management

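### For Grade 4 diarrhea that may be due to atezolizumab, Table 10 says resume and Appendix 13 says stop permanently, with no stated precedence

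*Combined protocol and SAP*

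**What the plan says.** Table 10 (Section 5.1.6.3), Grade 4 diarrhea, first withholds venetoclax, atezolizumab and chemotherapy. The trigger for restarting is "Upon resolution of Grade 4 diarrhea to Grade ≤ 1". Venetoclax then restarts one dose level lower, carboplatin and etoposide at 75%, and atezolizumab at its previous dose. The only approval named in the row is the Medical Monitor's, for re-escalating chemotherapy. A second branch covers uncontrolled Grade 4 diarrhea, or diarrhea of any grade needing hospitalization. It adjusts venetoclax and chemotherapy but does not mention atezolizumab. The two branches meet at "Administer atezolizumab at previous dose. For uncontrolled Grade 4 diarrhea".

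Appendix 13 Table 3, for Grade 4 diarrhea or colitis, says "Permanently discontinue atezolizumab and contact Medical Monitor.^c Refer patient to GI specialist for evaluation and confirmation biopsy". Its footnote c lets atezolizumab be considered again in patients who are deriving benefit and have fully recovered, and adds: "Patients can be re-challenged with atezolizumab only after approval has been documented by both the investigator (or an appropriate delegate) and the Medical Monitor".

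Section 5.1.6.3 sends sites to Table 10 and Appendix 13 in one sentence, which ends by directing holds and modifications to the drug judged the primary cause. On attribution of certain events it says "e.g., hepatotoxicity, skin and gastrointestinal toxicity) may be unclear when the agents are administered together". Where the investigator thinks "atezolizumab is a potential inciting factor, the dose of atezolizumab may be held for a maximum of 105 days beyond the last infusion", subject to exceptions approved by the Medical Monitor.

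The pointers elsewhere differ. Section 4.3.2.1 says "Guidelines for treatment interruption or discontinuation are provided in Appendix 10 and Appendix 13", while Section 4.3.2.3 says "Guidelines for treatment interruption or discontinuation are provided in Sections 4.6.1 and 5.1.5".

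**The concern.** The two tables give opposite default instructions for one drug, one event and one grade. A site working from Table 10 alone could restart atezolizumab as soon as Grade 4 diarrhea settles, even if immune-mediated colitis has not been excluded. A site working from Appendix 13 would stop the drug and could restart it only with two documented approvals. At stake is re-exposure after a possibly immune-mediated Grade 4 event without the approval that the protocol's own atezolizumab guidance requires.

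**Working it through.** No figure in the plan is involved, so the check is a comparison of texts.

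**1. The two instructions for Grade 4.**

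| | Table 10 | Appendix 13 Table 3 |
|---|---|---|
| First action on atezolizumab | Withhold | Discontinue permanently, contact Medical Monitor |
| After resolution to Grade ≤ 1 | Resume at previous dose | Taper steroids; atezolizumab stays stopped |
| Route back to atezolizumab | Resolution alone | Footnote c: benefit, full recovery, documented approval by both parties |
| Uncontrolled or hospitalized branch | No atezolizumab instruction | Not distinguished |

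**2. Can both apply to the same patient?** Yes. Section 5.1.6.3 lists diarrhea as an overlapping toxicity of all four drugs. Appendix 13 covers toxicities that are associated, or only possibly associated, with atezolizumab. An event judged to be mainly due to venetoclax, with atezolizumab not excluded, therefore falls under both. Section 5.3.4 (Table 12) leans the same way: an event counts as related unless there is evidence otherwise, and causality is assessed for each therapy. Appendix 13 also requires evaluation for other common causes. Where that work-up excludes atezolizumab, Table 10 stands without conflict.

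**3. Does other text settle it?**
- Section 5.1.6.3 gives no order of precedence. For a potential atezolizumab cause it provides a hold of up to 105 days, which is not permanent discontinuation. It says severe immune-mediated cases should be discussed with the Medical Monitor.
- Section 3.3.2.3 requires Medical Monitor approval of dose modifications. The Grade 4 row modifies venetoclax and chemotherapy, so the Medical Monitor should already be involved. Resuming atezolizumab at an unchanged dose is arguably not a modification, and documented approval of re-challenge is not mentioned.
- Section 5.1.5 gives the investigator discretion. Section 4.6.1 requires stopping for immune-mediated toxicity that the investigator finds unacceptable. Serious events are reportable within 24 hours (Section 5.4).

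None of these requires documented approval before re-challenge.

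**4. Comparison with the hepatic rows.** For Grade 3 and Grade 4 hepatic events, Table 10 discontinues atezolizumab, in line with Appendix 13 Table 2. The Grade 4 diarrhea row does not follow that pattern.

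**5. Grade 3 diarrhea.** Both sources resume atezolizumab. Appendix 13 Table 3 makes GI referral with biopsy and corticosteroids mandatory, and requires a taper of at least 1 month to ≤ 10 mg/day prednisone equivalent before resumption. Section 5.1.6.3 already suggests endoscopy and allows biopsies and systemic steroids. Section 5.1.5.2 already allows a hold until steroids are stopped or at ≤ 10 mg/day. What Table 10 and these sections lack is the mandatory wording and the minimum taper. Taking 1 month as at least 28 days, and steroids starting no earlier than the last infusion, resumption under footnote b is at day 28 or later. The next infusion is due at day 21, or 21 + 2 = 23 at the latest under Section 4.3.2. The gap is at least 28 − 23 = 5 days.

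**The case against.** The strongest reply is that the protocol already divides the work. Section 5.1.6.2 sends atezolizumab-specific events to Appendix 13, Table 10 deals with overlapping toxicities, and the primary-cause rule tells the site which drug to act on. Section 3.3.2.3 adds that, for overlapping toxicities including high-grade diarrhea, the aim is to preserve the dose intensity of atezolizumab and chemotherapy and to reduce venetoclax. On that reading, resuming atezolizumab is deliberate.

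Much of this stands. A reader might infer that every patient with Grade 4 diarrhea is returned to atezolizumab with no check on cause and no Medical Monitor involvement. The documents do not support that: the attribution rule precedes the table, and the dose changes in the same row need Medical Monitor approval. Where atezolizumab has been excluded as a cause, Table 10 is reasonable.

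The reply does not cover the unclear case. Primary cause and possible association are different thresholds, so one event can meet both, and Section 5.1.6.3 itself expects unclear gastrointestinal attribution. No text says that the primary-cause rule displaces Appendix 13 for a Grade 4 event.

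**Conclusion.** The conflict is real but limited to Grade 4 diarrhea in which atezolizumab is a suspected or unexcluded contributor. There, one row of Table 10 and one row of Appendix 13 Table 3 give opposite defaults, and the row's second branch leaves atezolizumab unaddressed. Existing safeguards reduce the risk but do not replace documented approval before re-challenge. The documents give no frequency of Grade 4 diarrhea on this regimen, so the number of patients affected cannot be stated.

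Two stronger readings should be avoided. A reader might infer an equal conflict at Grade 3; there both sources resume atezolizumab and only the taper length and mandatory wording differ. A reader might also infer that dose escalation is compromised, because Section 3.1.3 counts a treatment-related event requiring permanent discontinuation of a study drug as a DLT. Grade 3 or higher diarrhea lasting 72 hours or more despite adequate treatment is a DLT anyway. Any difference from that criterion is therefore confined mainly to shorter related Grade 4 events in the DLT period. With no frequency given, no effect on the MTD is claimed. No sample size, interval or endpoint changes.

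The conclusion assumes that sites treat Table 10 and Appendix 13 as equally binding, as Section 5.1.6.3 presents them.

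**What to change.** - **Table 10, Grade 4 diarrhea, both branches:** if immune-mediated diarrhea or colitis due to atezolizumab is suspected, or not excluded after work-up, Appendix 13 Table 3 takes precedence (permanent discontinuation, re-challenge only under footnote c). Otherwise, resume atezolizumab at the previous dose once the event is Grade 1 or better.
- **Section 5.1.6.3:** state the same precedence once, next to the primary-cause rule, so that the two are consistent.
- **Table 10, Grade 3 diarrhea:** add a cross-reference to Appendix 13 Table 3.

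The trigger should be a suspected or unexcluded immune-mediated cause. Requiring atezolizumab to be ruled out as any possible cause would clash with the primary-cause rule and would be hard to meet for a toxicity listed as overlapping for all four drugs.

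The cost is a few lines of text; Appendix 13 and Section 3.1.3 need no change. The downside is small: some patients with unclear attribution will stop atezolizumab or need documented approval to resume it.
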